### **Stage 2: Product evaluation**

We will conduct an evaluation of the Qlarity app with 380 high-risk adolescents who are involved in the juvenile justice system. Feasibility, usability, participant satisfaction, and intervention outcomes of substance use will be evaluated in an efficacy trial. Data on: 1) frequency and duration of app use, 2) number of modules completed, 3) changes in attitudes, emotions and behaviors, and 4) type and frequency of substance use will be examined. Participants will be compensated using gift cards to Amazon in the following increments: \$20 for each of the baseline, 4 week and 3-month assessments, and \$50 bonus for completion off all three assessments. Participants in the focus groups and usability testing will receive a \$30 gift card for their time and effort.

**Study Design:** Our evaluation of the program will be conducted with 380 adolescents ages 13- 18 who are referred from the Oregon Department of Youth Services (DYS) in Lane and Multnomah Counties, Oregon. Adolescents will be randomly and equally assigned to one of two conditions: 1) Qlarity, or 2) an active comparison condition that is standard treatment through the DHS (i.e., drug court, group therapy, and case management). All participants will be instructed to attempt to reduce substance use with a target quit date of 1 month after program initiation (day 28). Self-reported 7-day and 30-day point prevalence abstinence for all substances will be measured 1 and 3 months after treatment initiation. In addition, we will collect biochemical verification of self-reported substance use; urinary drug tests will be conducted at the baseline, 1- and 3-month follow ups and will follow the same UA drug testing protocol that we have found to be successful in our current NIH funded study with adolescents in the juvenile justice system.

**Participants:** Participants will include both male and female high risk adolescents recruited from the Department of Youth Services (DYS) in Lane and Multnomah Counties, Oregon. We have a long history of successful collaborations with the DHS and have received their support for the current proposal. Inclusion criteria will be as follows: 1) ages 13-18, 2) involvement with the juvenile justice system, 3) documented substance use, 4) English-speaking, and 5) living in the community (e.g., biological/adoptive/foster parents).

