**Statistical design and power overview:** This project will test the efficacy of the Qlarity app in Year 2 with a randomized trial that nests multiple assessments nested with 380 youth within each of two conditions. Half of the participants will receive the Qlarity app intervention and half will maintain business-as-usual. We hypothesize that Qlarity app will increase youth's emotional regulation, mindfulness and self-efficacy and decrease alcohol, tobacco, and other drug use. Within this study design, we will test for main effects, moderation, mediation, and acceptability of the Qlarity app intervention and expect to detect effect sizes of 0.25 standard deviations. Program feasibility will be demonstrated via significant pre-post differences, a high and consistent level of app use, and a high degree of youth satisfaction ratings. See Human Subjects Statistical Design and Power section for complete details.

**Feasibility benchmarks:** Program feasibility will be demonstrated by the achievement of the following benchmarks: (a) significant pre-post increases (e.g., Cohen's  $d > .35$ ) in emotional regulation, mindfulness, and self-efficacy, (b) significantly greater decreases in alcohol, tobacco, and other drug use for Qlarity participants; (c) a high consistent level of app usage (e.g., over 70% of users used the app at least 12 times over the 12 weeks); and (d) a high degree of youth satisfaction and ratings of app acceptability and usability (mean ratings  $> 4.0$  on the 5-point scale). Benchmarks are based on meta-analysis quantitative methods that recommend effect sizes of at least  $d > .25$  to demonstrate educationally meaningful change; a desire to show at least an average of weekly app use by a majority of participants; and a level of participant satisfaction that meets or exceeds that of Phase I.

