**Main-effects analyses.** Tests of the general effectiveness of the Qlarity app within this three-panel (pretest, 1- month, and 3-month follow-up) randomized trial requires an analysis that accounts for the dependence of multiple assessments nested within participants that were assigned to conditions. Thus, we will test most of our research hypotheses with random effects growth models within the hierarchical and structural equation modeling (SEM) frameworks with individual variability in change in study outcomes from pretest to 3-months nested within individuals. Following Singer and Willet when constructing the longitudinal model, we will (a) examine empirical growth plots; (b) fit an unconditional means model; (c) fit an unconditional linear growth model; (d) fit unconditional non-linear models; and (e) compare models of longitudinal change from the previous two steps using the Akaike Information Criterion. Individual variability change in the outcomes from baseline to the 3-month follow-up assessment will be modeled as a function of intervention condition. Intervention condition by time interactions will test whether groups differ on individual trajectories over the course of the study period. We will also use logistic regression models reporting odds ratios (OR) to test for differential rates of abstinence at the 3-month follow-up assessments with intervention condition a two-level predictor.

**Moderator effects.** Moderating effects of demographics (gender and minority status) and number of baseline offenses will be explored by adding the moderator to the random effects growth models described above. The multiplicative interaction term between the participant level moderators constitute a three-way cross-level interaction with time in the growth models and addresses whether the level of the baseline moderator impacted the magnitude of intervention condition on change in the outcome. All significant cross-level interactions will be probed by computing sample-estimated intercepts and slopes of the trajectories of the outcomes at conditional levels of the moderator, separately, within the Qlarity and usual care group (i.e., simple trajectories) using methods described by Curran (Curran, Bauer et al. 2006).

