**Power considerations.** The assumptions for the power estimates include a sample size of 380 participants, Type II error rate of 20% ( $\beta = .20$ ) and a 2-tailed alpha = .05. Power estimates for multilevel growth models require assumptions that are not easily established in longitudinal studies (e.g., complete data, homogeneous random-effects covariance structures within conditions). Thus we rely on the fact that power for multilevel growth models has been shown to surpass that of the mixed-model ANCOVA. The proposed growth models, then, will detect smaller differences between conditions than the ANCOVA models on which power estimates were based. Allowing for intent-to-treat analyses that makes use of all available data using missing data techniques described above and a pretest covariate  $r^2 = .25$ , there is sufficient power to detect main effects for condition of Cohen's  $d = .25$  (small effect size) and detect condition by moderator effects of  $d = .35$  (small to medium effect). The smallest subsample expected for decomposition of significant moderating effects is approximately 150 minority participants (75 per condition) which will provide sufficient power ( $>.80$ ) to detect condition effects of  $d = .40$  (medium effect). The study is also powered to detect small to medium between condition effect size differences (ORs = 2.05 – 2.25) for the logistic regression models predicting an estimated 15-20% substance use abstinence rates at follow-up. Using mediation effect size guidelines from Kenny for a model containing a dichotomous independent variable and a continuous mediator, effect sizes of .02, .15, and .40 derived from the product of  $d$  and  $r$ , represent small, medium, and large effect sizes respectively. Assuming small to moderate effects for the indirect pathway ( $r = .20$ ), the proposed sample size has sufficient power ( $>.94$ ) to detect small effect sizes or greater ( $dr = .04$ ) for tests of mediation. Process analyses involving correlation coefficients will have adequate power to detect small to medium effects ( $r = .20$ ).

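### The power overview quotes one detectable effect of 0.25 SD for all its tests, but the detailed power paragraph supports 0.25 only for the pretest-adjusted continuous main effect, giving d = .35 for moderation and OR 2.05–2.25 for abstinence

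*Combined protocol and SAP*

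**What the plan says.** The paragraph headed Statistical design and power overview states that the study will "test for main effects, moderation, mediation, and acceptability of the Qlarity app intervention and expect to detect effect sizes of 0.25 standard deviations". No test or outcome is excepted, and the paragraph ends by pointing to a fuller power section.

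The paragraph headed Power considerations, under Data Analysis, is more specific. Its basis is "The assumptions for the power estimates include a sample size of 380 participants", "2-tailed alpha = .05" and a "Type II error rate of 20" percent. On an ANCOVA basis with pretest r² = .25, "there is sufficient power to detect main effects for condition of Cohen's" d = .25. It then gives:

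- d = .35 for condition-by-moderator effects;
- d = .40 for condition effects among about 150 minority participants (75 per condition);
- "between condition effect size differences (ORs = 2.05 – 2.25) for the logistic regression models", at an estimated abstinence rate of 15–20%.

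The logistic models appear under Main-effects analyses, where they "test for differential rates of abstinence at the 3-month follow-up assessments with intervention condition a two-level predictor". The abstinence comparison is therefore one of the main effects to which the overview's sentence applies.

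**The concern.** The overview and the detailed paragraph give different sensitivities for the same tests. For moderation the conflict is direct, .25 against .35, and needs no conversion. For abstinence the plan prints an odds ratio and never relates it to 0.25 SD, so a reader of the overview cannot tell that the abstinence test needs a larger effect than the headline figure suggests.

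Interpretation is what is at stake. The trial sets a target quit date at day 28, measures abstinence at 1 and 3 months with urine testing, and is meant to supply power estimates for a later, larger evaluation. A reader who takes 0.25 SD as the sensitivity of every test could read a non-significant interaction or abstinence odds ratio as evidence against an effect of that size, when the design had limited ability to detect one.

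**Working it through.** **Inputs.** N = 380 and two-sided α = .05 with 80% power (Power considerations); equal allocation, "Adolescents will be randomly and equally assigned to one of two conditions" (Study Design), so 190 per arm; pretest r² = .25, d = .25, .35 and .40, 75 per arm in the minority subsample, OR 2.05–2.25 and abstinence 15–20% (Power considerations); 10% non-completion, leaving 342, or 171 per arm (Data Collection Procedures).

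**1. Continuous outcomes.** Power = Φ(d / [√(1 − r²) · √(2/n)] − 1.96), with n per arm and √(1 − .25) = .866.

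- Main effect, n = 190: .25 / (.866 × .1026) = 2.814, so power = Φ(.854) = 80.3%. The plan's d = .25 reproduces.
- Moderation read as a condition effect in half the sample, n = 95: at d = .35, .35 / (.866 × .1451) = 2.785, power 79.5%. This reading reproduces the plan's .35. At d = .25 the ratio is 1.990, power 51%.
- Minority subsample, n = 75: at d = .40, .40 / (.866 × .1633) = 2.828, power 80.7%, which reproduces the plan. At d = .25 the ratio is 1.768, power 42%.

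The plan does not define what its .35 measures. If it is the difference between two half-sample effects, the standard error is .866 × √(4/95) = .178. Power at .25 is then 29%, and the effect detectable with 80% power is about .50.

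**2. The printed odds ratios.** On the logistic standard error, the OR detectable with 80% power is exp(2.802 / √[N × .25 × p(1 − p)]), with p the overall abstinence rate.

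- p = .15: exp(2.802 / √12.11) = 2.24.
- p = .20: exp(2.802 / √15.2) = 2.05.

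These match the printed 2.25 and 2.05. Reading 15–20% as the control-arm rate gives 2.06 and 1.94 by a two-proportion test, which fits less well. The apparent basis is therefore an overall rate with all 380 analysed. The implied arm rates are 10% vs 20% (OR 2.25, overall 15%) and 14.4% vs 25.6% (OR 2.05, overall 20%). A pooled two-proportion test at those rates has 78.2% and 78.4% power, close to 80%.

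**3. Abstinence at 0.25 SD, logistic scale (an assumption not in the documents).** d = ln(OR) × √3/π puts OR 2.05 at .396 and OR 2.25 at .447. Conversely, 0.25 SD is OR = exp(.25 × π/√3) = 1.57. Two-proportion power at OR 1.57 is:

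| 15–20% read as | Analysed | At 15% | At 20% |
|---|---|---|---|
| Overall rate | 380 | 34.5% | 41.7% |
| Overall rate | 342 | 31.6% | 38.3% |
| Control-arm rate | 380 | 39.5% | 46.6% |
| Control-arm rate | 342 | 36.2% | 42.8% |

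The range is about 32–47%. Dividing ln(OR) by 1.65 instead (Cox) makes 0.25 SD an OR of 1.51 and lowers power further.

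**4. Abstinence at 0.25 SD, SD of the 0/1 outcome.** The difference is .25 × √[p(1 − p)], which is 8.9 percentage points at 15% and 10 points at 20%. Power is about Φ(.25/√(2/190) − 1.96) = Φ(.477) = 68% with 380, and Φ(.25/√(2/171) − 1.96) = Φ(.352) = 64% with 342.

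**The case against.** The strongest reply is that the plan's two main figures agree with each other. On the SD of the 0/1 outcome, 10% vs 20% is .10/√.1275 = .280 and 14.4% vs 25.6% is .281. The unadjusted effect detectable with 190 per arm is .287, and .287 × .866 = .249, which is the plan's d = .25. On that scale the abstinence test has about the same sensitivity as the continuous test, less the pretest covariate. The reply also notes that the overview is a summary that refers to a fuller section, that Power considerations prints the odds ratios, labels them small to medium and never claims 0.25 SD for abstinence, and that most hypotheses are to be tested with growth models, with the logistic models added to them.

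Most of this stands, and it rules out two stronger readings. A reader might infer that the odds ratios simply are 0.40–0.45 SD, so that the abstinence test has only about 35–42% power at the trial's target and would miss more often than it succeeds. The documents do not support this: they give no conversion, and on the 0/1 scale power is 64–68%. A reader might also infer that the power calculation is wrong or that the abstinence sensitivity is concealed. Neither is so, since the figures are printed and reproduce approximately.

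The reply does not rescue the overview's sentence. The moderation conflict depends on no scale, and power for abstinence at 0.25 SD is below 80% on every scale checked.

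**Conclusion.** The concern holds as an inconsistency between a summary sentence and the detailed paragraph behind it. A detectable effect of 0.25 SD is supported only for the continuous condition main effect with pretest r² = .25 and N = 380. For moderation the plan's own figure is .35, and power at .25 is about 51% on the reading that reproduces it. In the minority subsample the plan's figure is .40, and power at .25 is about 42%. For abstinence the plan's figure is OR 2.05–2.25, or roughly 10% vs 20% to 14% vs 26% on its apparent basis. Power at 0.25 SD is about 32–47% on the logistic scale and 64–68% on the 0/1 scale.

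The abstinence percentages depend on the scale, on whether 15–20% is the overall or control-arm rate, and on whether 342 or 380 are analysed; the direction does not. No shortfall is claimed for mediation: the plan's dr = .04 with r = .20 implies d = .04/.20 = .20, below .25. That calculation was not re-run, and acceptability was not tested against 0.25 SD. Severity is minor.

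**What to change.** In the overview, limit 0.25 SD to pretest-adjusted main effects on continuous outcomes. Beside it, quote d = .35 for moderation, d = .40 for the minority subsample, and OR 2.05–2.25 for the logistic models, with the implied abstinence rates (about 10% vs 20% at 15% overall; 14% vs 26% at 20% overall).

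In Power considerations, say whether 15–20% is the overall or control-arm rate and what the moderation d of .35 measures. State that the moderation and abstinence tests have less than 80% power at 0.25 SD, naming the scale and rate assumptions. Add that a non-significant result on either will be reported with its confidence interval and not read as no effect.

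The cost is a few sentences in two paragraphs and a less favourable stated sensitivity. No new data, participants or analyses are needed.

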**Focus Groups and Usability Testing:** Twenty high-risk adolescents will be recruited to participate as test users in the development phase to give us initial reactions to mockup of modules, and a subgroup of 10 of these participants will be recruited to participate in preliminary usability testing of the modules. Feedback from usability testing will be used to inform adaptations to the app. The prototype app will then be evaluated in an efficacy trial with 380 additional high-risk adolescents. The primary outcomes of the evaluation-testing phase will be changes in adolescent substance use attitudes and behaviors and emotion regulation measured at three time points: baseline, 4 weeks post- baseline (end of treatment), and three months post-baseline. The proposed efficacy trial will evaluate the extent that the Qlarity app influences positive behavior change and will provide power estimates for later larger scale evaluation.

**Efficacy Trial:** Based on our power calculations, we will recruit 380 adolescents who are involved in the juvenile justice system. We have a long history of cooperation with the DHS and have well-established recruitment procedures. Eligible adolescents and their consenting parents will be recruited on a continual basis and will be included in the study for 3 months post-baseline. The participants will be randomly and equally assigned to the Qlarity condition ( $n = 190$ ) or the DC standard treatment condition ( $n = 190$ ) following adolescent assent and parent consent. Given that all youth will be involved in the juvenile justice system, we will assess all services offered and accessed by youth in both conditions.

Based on our prior experience, we expect many of the youth to be under orders to be participating in urine screening or other intervention services through DHS. Data from our current and prior studies with this population suggest that despite receiving random urine screens as part of their probationary status, 90% of youth are involved in ongoing alcohol, tobacco or other drug use (79% alcohol; 68% tobacco; 81% marijuana, and 53% other drug; 90% positive for one or more substance) at the time of referral. We will track additional services, including mandated urine screens, via official DHS reports and using a services utilization measure at each follow-up time point.

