### **Overview of the Proposed Intervention Conditions**

We propose to randomize youth into one of two conditions, outlined below.

**Qlarity.** Subjects randomized to Qlarity will be provided in-person assistance in loading the Qlarity app onto their phone immediately following their baseline interview and assessment. Once the app is loaded onto their phone, participants will generate a username and password. The proposed modules will each include a teaching and a practice component that uses mindfulness techniques to reduce or avoid substance use. Modules will be “unlocked” in ascending order as participants move through the program (i.e., module 2 will be “unlocked” after completion of module 1, etc.).

**Drug Court, Group Therapy and Case Management (DC).** The DC youth will receive the usual services provided by the DHS for youth who present with drug and alcohol use, which includes involvement in drug court, and case management services for the youth and their parents that span the duration of the youth’s probation or formal accountability contract. The drug court and case management services are provided by probation officers through the DHS. The DHS will manage each case and will make all decisions on referrals to community resources, including individual therapy, family therapy, mandated urine screens, and/or inpatient or outpatient substance use treatment that might occur in addition to the typical youth skill building groups and case management services. None of the usual services that youth in the respective study conditions receive will be affected by their participation in the study. We will track the youths’ and parents’ use of services as part of the interviews with a service utilization measure and official DHS reports of urine screens at each assessment. With these data, we will examine the type and length of treatment received for youth in both conditions, as well as the timing and outcome of urine screens over the course of the study. This services utilization measure has been used in previous work and has been useful for examining treatment impact.

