**Feasibility benchmarks.** Program feasibility will be demonstrated by the achievement of the following benchmarks: (a) significant pre-post increases (e.g., Cohen's  $d > .35$ ) in emotional regulation, mindfulness, and self-efficacy, (b) significantly greater decreases in alcohol, tobacco, and other drug use for Qlarity participants; (c) a high consistent level of app usage (e.g., over 70% of users used the app at least 12 times over the 12 weeks); and (d) a high degree of youth satisfaction and ratings of app acceptability and usability (mean ratings  $> 4.0$  on the 5-point scale). Benchmarks are based on meta-analysis quantitative methods that recommend effect sizes of at least  $d >.25$  to demonstrate educationally meaningful change; a desire to show at least an average of weekly app use by a majority of participants; and a level of participant satisfaction that meets or exceeds that of Phase I.

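### Feasibility benchmark (a) is an uncontrolled pre-post change, so an app with no effect can meet it; it should be a Qlarity-versus-DC comparison

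*Combined protocol and SAP*

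**What the plan says.** The benchmarks appear twice in the combined protocol and SAP, in the same words: after the paragraph on statistical design and power, and at the end of Data Analysis. Item (a) asks for significant increases from before to after, with a Cohen's d above .35 offered as an example. No arm or comparator is named. The sentence then moves to a comparative item: "in emotional regulation, mindfulness, and self-efficacy, (b) significantly greater decreases in alcohol, tobacco, and other drug use for Qlarity participants". Items (c) and (d) concern app use and satisfaction.

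The overview sentence that introduces feasibility is shorter. It begins "Program feasibility will be demonstrated via significant pre-post differences", adds app use and satisfaction, and leaves out item (b).

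On background care, the Overview of the Proposed Intervention Conditions states: "None of the usual services that youth in the respective study conditions receive will be affected by their participation in the study". Study Design adds that all participants are told to try to reduce use towards a quit date. On design, "The participants will be randomly and equally assigned to the Qlarity condition" or to the DC condition, 190 each. Table 1 schedules the emotion regulation, mindfulness and alcohol and drug use measures at baseline, 1 month and 3 months with no difference by arm. The Measures text places the self-efficacy scale inside the last of these.

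**The concern.** A pre-post change in one arm is not an app effect when other things are happening to the same youths. Here the change would contain usual services, the instruction to cut down, the effect of answering the same questionnaires again, and the passage of time. The randomised DC arm exists to remove those components and supplies the data to do so, but item (a) does not use it.

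Item (b) does not close the gap, because it covers only alcohol, tobacco and other drug use. No benchmark is controlled for the three constructs in (a), although the plan hypothesises that the app will raise them and lists emotion regulation among the primary outcomes. Read alone, the overview sentence would allow feasibility to be declared with no comparison between arms at all.

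**Working it through.** **Inputs.** From Power considerations: "a sample size of 380 participants", "2-tailed alpha = .05", 80% power, between-arm d = .25 and pretest r² = .25. From the Data Collection overview: 10% loss, leaving 342 completers, or 171 per arm if losses are equal.

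**The plan's own figure first.** With covariate adjustment the residual SD is sqrt(1 − .25) = .866.
- SE of the between-arm difference at 190 per arm: .866 × sqrt(2/190) = .0889.
- Power at d = .25: Phi(.25/.0889 − 1.96) = .803. The stated 80% reproduces.
- With 171 per arm, power is .761.

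**Benchmark (a) with an inert app.** Assumptions: (a) is applied to the Qlarity arm; the SD is equal before and after; the pre-post correlation is r = .5, the square root of the plan's r².
- SE of the pre-post d = sqrt(2(1 − r)/n) = sqrt(1/171) = .076.
- The smallest significant observed d is 1.96 × .076 = .15.
- P(significant increase) = 1 − Phi(1.96 − b/.076), where b is the background change.
- P(observed d > .35) = 1 − Phi((.35 − b)/.076).

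The documents give no value for b, so a range is shown, per outcome:

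| Assumed b | Significant increase | Observed d > .35 |
|---|---|---|
| 0 | 2.5% | under 0.1% |
| .10 | 25.7% | 0.1% |
| .20 | 74.4% | 2.5% |
| .30 | 97.5% | 25.7% |
| .35 | 99.6% | 50% |
| .45 | over 99.9% | 90.5% |

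Sensitivity to r at b = .20: the chance of significance is 60% for r = .3 and 92% for r = .7. With all 190 analysed and r = .5 it is 79%.

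**All three outcomes together** (190 in the arm, r = .5, assumed correlation between outcomes 0 to .5):
- All significant at b = .20: 49% to 59%.
- All above .35: 12% to 25% at b = .35, and 77% to 81% at b = .45.

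**The same benchmark as a between-arm test.** Background change common to both arms cancels. An inert app then reaches significance in the favourable direction 2.5% of the time per outcome, whatever b is.

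**The case against.** The strongest reply is that little depends on (a). The benchmarks form a list of four, and (b) is comparative, so an inert app that passed (a) would still have to pass (b). The Main-effects analyses test outcomes by condition-by-time interaction, and the power statement is between conditions. This stands: the efficacy conclusion is not affected, and no stated number is wrong. It does not answer the point that (b) covers other outcomes, or that the overview sentence omits (b).

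Several stronger readings are tempting, but the documents do not support them.
- *Every youth receives drug court, therapy, case management and mandated screens.* The plan expects many, not all, to be under orders for screening or other services, and leaves therapy referrals and mandated screens to DHS case by case. The drug court package is described for the DC arm; its presence in the Qlarity arm follows only from the statement that usual services are unaffected.
- *Item (a) is a go/no-go rule.* The text says only that meeting the benchmarks will demonstrate feasibility.
- *Regression to the mean is shown by the 90% using at referral.* That figure concerns substance use. Eligibility does not select on the scales in (a), so such regression is possible but not documented.
- *Item (a) would reject an app that works as targeted.* With a true effect of .25 and no background change, the .35 cut is met about 10% of the time, but .35 is only an example. On significance alone the same app passes about 90% of the time.

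**Conclusion.** The point holds as a defect in one feasibility benchmark and in the overview sentence. As written, (a) can be met by an app with no effect. How likely that is rests on a background change that the documents do not give: negligible risk at zero, about three in four per outcome on significance at d = .20, and an even chance on the .35 example only if background change is itself about .35. The chances are lower if all three outcomes must pass. The figures assume r = .5, equal SDs and 171 completers. A reader might infer that the trial's efficacy result is compromised; it is not, because those tests compare the randomised arms.

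**What to change.** In both statements of the benchmarks, restate (a) as a significantly greater increase in Qlarity than in DC on each of the three outcomes, taken from the condition-by-time models in Main-effects analyses. Make between-condition significance the criterion rather than a cut on the observed d: a cut at .25 would be met only about half the time when the true difference is .25. Report within-arm pre-post d for both arms as description only. Align the overview sentence with the full (a) to (d) list.

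This is a change of wording, with no new data, visits or models. The cost is a harder benchmark. Power per outcome at a true between-arm d of .25 is about .80 with 190 per arm and .76 with 171. Requiring all three lowers it: if the outcomes were independent, .803³ = .52 and .761³ = .44, with higher values if they are positively correlated.
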